### 7.3 LOST TO FOLLOW-UP

A participant will be considered lost to follow-up if he or she fails to return for the 12 month study visit and is unable to be contacted by the study site staff.

The following actions must be taken if a participant fails to return to the clinic for a required study visit:

- The site will attempt to contact the participant and reschedule the missed visit within 30 days and counsel the participant on the importance of maintaining the assigned visit schedule and ascertain if the participant wishes to and/or should continue in the study.
- Before a participant is deemed lost to follow-up, the investigator or designee will make every effort to regain contact with the participant (where possible, 3 telephone calls and, if necessary, a certified letter to the participant's last known mailing address or local equivalent methods). These contact attempts should be documented in the participant's study record.
- Should the participant continue to be unreachable, he or she will be considered to have withdrawn from the study with a primary reason of lost to follow-up.

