## 1.2 SCHEMA

## 1.3 SCHEDULE OF ACTIVITIES (SOA)

Study Procedures	En.	Days from Enrollment															
		-14 to 0	0	7	9	30	60	90	120	150	180	210	240	270	300	345	365
Study Window (days)			+ 4	-1 to +5	±14	±14	±14	±14	±14	±14	±14	±14	±14	±14	±14	±14	±14
Baseline Study Visit*		x															
Follow-up Study Visits*											x						x
Consent		x															
Eligibility		x															
Review inclusion/exclusion criteria		x															
PAR-Q Screen (11.1)		x															
Medical Clearance Letter (11.2) if positive PAR-Q screen		x															
Survey Response Collection Method (text, email, in-person)		x															
Reminder phone call, text message, or email prior to visit											x						x
Physical Activity Measurement																	
Actigraph device and instructions provided		x															
ActiGraph wear (consecutive 7-day periods with remote CentrePoint Sync app upload)		x			x	x	x	x	x	x	x	x	x	x	x	x	
Reminder email/phone call/text message (Actigraph instructions)**				x	x	x	x	x	x	x	x	x	x	x	x	x	
Collect Actigraph device and charger from participant																	x
Anthropomorphic Measurements																	
Height		x															
Weight		x									x						x
Laboratory Measurement																	
Screening hemoglobin A1C (point-of-care sample)to -1		x									x						x
Repeat A1C (serum or alternative POC A1C device) if suspected erroneous A1CNow+ reading		x									x						x
Randomization																	
Referral to hDPP		x															
Mail Sweetch digital health kit (research coordinator)			x														

Study Procedures	-14 to 0	0	En.	Days from Enrollment														
				7	9	30	60	90	120	150	180	210	240	270	300	345	365	
Study Window (days)				+4	-1 to +5	±14	±14	±14	±14	±14	±14	±14	±14	±14	±14	±14	±14	
Download/register Sweetch app + sync scale (participant)				x														
Questionnaires/Surveys (text, email, in-person)																		
Demographics (11.3)		x																
Medical history and medications (11.4)		x									x						x	
Exercise stage of change questionnaire (11.5)		x									x							
Self-reported PA information (11.6)**		x			x	x	x	x	x	x	x	x	x	x	x	x		
"Starting the Conversation" Brief Dietary Assessment (11.7)		x									x						x	
Apps and Devices (11.8)		x																
NPART Survey (11.9)		x																

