### 5.6.3 MINIMIZING PARTICIPANT BURDEN

We have designed the study to minimize participant burden. The option of home study visits will be provided for participants enrolled at the JHU site, which we expect will increase recruitment yield by making the study more convenient for participants. We will initially conduct home study visits during weekdays and daylight hours, but may consider weekend visits if needed to

increase enrollment rate. If participants report challenges making it to the research clinic site for follow-up visits due to scheduling conflicts, we will consider adding non-business and weekend hours to accommodate participant's schedules as much as possible. After a participant is enrolled in the study, research staff will be expected to follow our Difficult to Reach Protocol (Section 5.6.5). All attempts to contact, including the failed attempts and the outcome of the attempts, will be documented in the electronic case report form. A copy of the letter(s) sent to the participants will be saved in the case report form.

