## 5.6.5 DIFFICULT TO REACH PROTOCOL

A total of 10 contact attempts are made to all the phone numbers provided by the participant at varying times of the day. The calls may be divided in the following manner: 2 calls before 11 AM, 2 calls between 11 AM and 3 PM, 2 calls between 3 PM and 6 PM, 2 calls after 6 PM, and 2 calls on the weekend.

- a) At least 5 text messages are sent.
- b) At least 5 emails are sent – if email provided.
- c) One “unable to contact letter” is sent to the home address. The letter must contain name and address of the participant, visit, compensation amount, date, name and contact information of the study team member.
- d) Attempt to contact 1-3 alternative contact(s); defined for the participant as ‘someone who will know how to reach you.’

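### Section 7.3 defines loss to follow-up at 12 months but lets its withdrawal step follow any missed visit, with a weaker contact standard than 5.6.5, so obtainable 12-month outcomes could be excluded

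*Combined protocol and SAP*

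**What the plan says.** Section 7.3 opens with a definition: "A participant will be considered lost to follow-up if he or she fails to return for the 12 month study visit" and, in addition, site staff cannot make contact. The next sentence has a wider trigger: "The following actions must be taken if a participant fails to return to the clinic for a required study visit". The Schedule of Activities (1.3) places "Follow-up Study Visits" at day 180 and day 365, so month 6 is a required visit.

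The action list has three steps. The site tries to make contact and rebook within 30 days. Before declaring anyone lost it makes every effort, illustrated in parentheses as "3 telephone calls and, if necessary, a certified letter". Finally, "Should the participant continue to be unreachable, he or she will be considered to have withdrawn from the study", with loss to follow-up recorded as the primary reason.

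Other sections bear on the same decision:

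- 5.6.5: "A total of 10 contact attempts are made to all the phone numbers provided by the participant at varying times of the day", plus at least 5 texts, at least 5 emails where an address is held, one letter, and 1 to 3 alternative contacts.
- 5.6.3: once someone is enrolled, "research staff will be expected to follow our Difficult to Reach Protocol", with every attempt documented in the case report form.
- 7.2: the team withdraws a participant only where continuing would not be in that person's best interest. Being unreachable is not named.
- 7.1: participants who do not engage with either programme are to be kept in the study for outcome assessment.
- 9.3: analysis is by randomised group, but people who withdraw from the study or withdraw consent are left out of the effectiveness analyses.

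**The concern.** The definition and the action list have different triggers, and only the definition mentions month 12. A site that works down the list after a missed 6-month visit can reach withdrawn status well before the primary endpoint is due. The section that assigns the status also describes a lighter contact effort than 5.6.5 and does not refer to it.

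The label matters because of 9.3: a randomised participant classed as withdrawn leaves the primary comparison. Imputation does not clearly bring that person back. Section 9.4.2 ties multiple imputation to missing physical activity data and discusses weight and A1C only for study completers. Staff who pursue missing participants know the arm (6.4), so uneven pursuit could make exclusion differ between arms.

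**Working it through.** **1. Triggers side by side.** Lost to follow-up needs a missed 12-month visit and failed contact. The action list needs only a missed required visit (day 180 or day 365). The last step needs only continued failure of contact. Read literally, the last step can be reached after day 180.

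**2. Timing.** 365 − 180 = 185 days from the 6-month to the 12-month visit. Less the 30-day rebooking period, 155 days remain. The label could therefore be applied about 5 to 6 months before the primary assessment.

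**3. What the 6-month visit contributes to the primary endpoint (3.2).**
- 5% weight-loss route: baseline and 12-month weight.
- A1C route: baseline and 12-month A1C, if baseline is 5.7% to 6.4%.
- 4% weight-loss route: baseline and 12-month weight, plus Actigraphy averaged over months 1 to 11.

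No route uses measurements taken at the 6-month visit. Someone out of contact from month 6 may, however, lack later Actigraphy, which affects the 4% route.

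**4. Contact standards.** Section 7.3 illustrates 3 calls and a possible certified letter. Section 5.6.5 has 10 call attempts, texts, emails, a letter and alternative contacts. Completing 5.6.5 would exceed the calls in 7.3. Stopping at the 7.3 illustration would not complete 5.6.5.

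**5. The plan's sample size (9.1, 9.2).** Inputs: 50% success in both arms, 15-point margin, one-sided 5%, 80% power, 25% attrition.

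n per arm = (1.645 + 0.842)² × 2 × 0.5 × 0.5 / 0.15² = 137.4, rounded up to 138. Then 138 / 0.75 = 184 per arm, 368 in total. Both figures reproduce.

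**6. Power at other losses.** Power = Φ(0.15 / √(2p(1−p)/n) − 1.645), with n = 184 × (1 − loss). The 35% column is the middle of the 30–40% control rate expected in 9.1.

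| Loss | p = 50% | p = 35% |
|---|---|---|
| 25% | 80.2% | 83.3% |
| 30% | 77.7% | 81.0% |
| 35% | 75.0% | 78.4% |
| 40% | 72.0% | 75.5% |

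Beyond the 25% allowance at p = 50%, 5 more losses per arm give 78.9%, 10 give 77.5% and 20 give 74.5%.

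**7. Unequal exclusion (illustration; loss rates and success among the excluded are assumptions).** Let true success be 35% in both arms, m the share excluded, and s the success rate among the excluded. Observed rate = (0.35 − m·s) / (1 − m).

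- 25% lost in both arms, s = 10%: 43.3% in each, difference 0.
- hDPP 20%, dDPP 30%, s = 10%: 0.33/0.80 = 41.2% and 0.32/0.70 = 45.7%, a spurious 4.5 points for dDPP.
- Same losses, s = 20%: 0.31/0.80 = 38.7% and 0.29/0.70 = 41.4%, 2.7 points.
- hDPP 15%, dDPP 35%, s = 10%: 39.4% and 48.5%, 9.0 points.

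Swapping the arms reverses the sign. These are total losses by arm. The part due to the wording of 7.3 is unknown.

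**The case against.** The strongest reply is that 7.3 should be read as a whole. Its last step records loss to follow-up as the reason, a term the section has just defined by a missed 12-month visit, and its second step also speaks of deeming someone lost. On that reading only the rebooking step applies at month 6, and nobody can be lost before month 12. Sections 7.1 and 7.2 also point against early closure, and no text cancels the 12-month visit after a missed 6-month visit. This is a fair reading and may be the intended one. It does not remove the problem, because the mandatory list has the wider trigger and its final step does not repeat the limit.

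A reader might infer that coordinators may choose 3 or 10 attempts and comply either way. The documents do not support that: 5.6.3 expects staff to follow 5.6.5, and 7.3 itself asks for every effort, so stopping at three calls departs from the protocol. Different effort by arm is a possibility in an open-label trial, not something the plan permits.

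A reader might also infer that the primary endpoint needs only baseline and 12-month weight and A1C. That holds for two routes, but the 4% route also needs Actigraphy.

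**Conclusion.** Section 7.3 is internally inconsistent about when an unreachable participant becomes withdrawn. It states a lighter contact effort than 5.6.5, and its withdrawal step does not fit 7.2. Through 9.3, one literal reading could remove participants whose 12-month weight and A1C were still obtainable.

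The stronger statement, that such outcomes are lost, goes further than the text: it depends on sites adopting one of two available readings. Nor can a number of lost outcomes be given, because the documents report neither how many would miss month 6 and stay unreachable nor how many of those would attend at month 12.

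No power shortfall is shown. Losses within the 25% allowance leave power at about 80%, and power falls below that only if total loss goes beyond the allowance (beyond 30% if success is about 35%). The more important risk is unequal exclusion: 2.7 to 9.0 points in the assumed cases, against a 15-point margin, and zero if losses and outcomes among the lost are alike in both arms. The exclusion rule in 9.3 is a separate matter, and amending 7.3 would not change it.

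**What to change.** Amend 7.3 in three places:

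1. State that a missed 6-month visit does not make a participant lost or withdrawn, and that the 12-month visit is still pursued unless the participant withdraws consent or is withdrawn under the protocol's other withdrawal provisions, which stay as they are.
2. Limit the final step to participants who have missed the 12-month visit.
3. Replace the parenthetical on calls and a letter with a cross-reference to completing the 5.6.5 sequence, logged and applied identically in both arms.

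The cost is a wording amendment. The contact effort is already required by 5.6.5, and 5.6.3 already asks for it to be documented.

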### 7.4 PARTICIPANT STUDY END DEFINITION

[figure not shown]
A participant will be considered "off-study" (i.e. completer) when all of the following criteria are satisfied:

- Completion of the 12 month study visit
- *For hDPP arm only:* 12 months have elapsed from the date of the first visit in the hDPP. If participant never attends a hDPP, this criterion is not applicable.

## 8 STUDY ASSESSMENTS AND PROCEDURES

For the JHU site, participants who express interest in the study will be offered the option of home study visits or on-site study visits. Home study visits will be conducted during daylight hours in accordance with a defined safety protocol (Section 11.19).

## 8.1 STUDY CONSORT DIAGRAM

## 8.2 EFFECTIVENESS ASSESSMENTS

At the study visits, the following procedures and evaluations will be performed by a trained research coordinator according to the Schedule of Activities (Section 1.3):

### 8.2.1 PHYSICAL EXAMINATION

Height will be recorded to nearest 0.1 cm using a portable stadiometer. Weight will be recorded to the nearest 0.1 kg using a portable digital scale. The same scale will be used for all participants for each measurement. Participants will be asked to wear light clothing, remove shoes, and void prior to weight measurements.

### 8.2.2 LABORATORY EVALUATIONS

In this study, we will be using A1C testing for two purposes: a) safety (ruling out diabetes at screening visit) and b) measuring change in A1C (one of the composite endpoints of the study). Considering that some participants could have progressed from prediabetes to diabetes since their last A1C test, a repeat A1C test will be obtained at the screening visit for safety reasons to exclude patients with possible type 2 diabetes (A1C of 6.5% or greater). Such participants will be ineligible to join and will be advised to contact their primary care provider for confirmatory diagnostic testing.

For participants who have not had a laboratory test to confirm the diagnosis of prediabetes as specified in our inclusion criteria (Section 5.1), the POC A1C measurement will be used for screening purposes to ascertain eligibility, and a result between 5.7% and 6.4% would render the participant eligible. For example, if a participant had an A1C result two years ago of 6.2% but has not had a repeated A1C test or fasting glucose in the past year, the screening test would be done to determine prediabetes status.

The second reason for the A1C test will be to determine change in A1C at 6 months and 12 months from the baseline study visit, which is one of the composite endpoints of our study. Of note, the CDC has defined reduction in A1C of 0.2 or more at 1 year to be an indicator of success in the DPP. This outcome measure (a component of our composite endpoint) will be limited to participants whose baseline A1C (obtained by our study team) is between 5.7% and 6.4%.

A1C will be obtained using FDA cleared, CLIA-waived, and NGSP-certified devices (Afinion™ 2 Analyzer, Siemens DCA Vantage, or A1CNow+ test kit). These point-of-care tests require a fingerstick blood sample and an A1C result is obtained in 5 minutes. All A1C testing will be performed by a trained research coordinator.

The A1CNow+ test is a portable testing device that can be used for home study visits. While this device is FDA approved and NGSP certified, it has larger mean bias from laboratory-obtained gold standard compared to the Afinion Analyzer and Siemens DCA vantage machines; in addition, this testing device is more susceptible to interference from hemoglobinopathies (e.g. sickle cell trait or disease) and the presence of rheumatoid factor. For study participants who request a home study visit, a screening protocol will be followed to exclude conditions that could lead to interference with the A1CNow+ test (Section 11.18). If the participant has an underlying condition that could interfere with the accuracy of the A1CNow+, they will be offered a study visit at the clinical research unit, where testing can be performed using more accurate devices that are not prone to interference from these conditions (Afinion™ 2 Analyzer or DCA Vantage). If a quality control error message is received using any of the point-of-care testing devices, the test will be repeated with a second sample. A1CNow+ failure will be defined as two quality control or error messages during a study visit. In addition, an A1CNow+ reading that differs from an A1C obtained in the past 3 months by less than or equal to -0.9 points or greater than or equal to 0.8 points (outside the 95% confidence interval of A1CNow+ test compared to venous sample A1C), could suggest possible unrecognized interfering condition (hemoglobinopathy or rheumatoid factor) resulting in a spurious result. In this case, the participant will be offered repeat screening with an alternative A1C testing method, either point-of-care test conducted in the clinical research unit or serum A1C measurement obtained at a Labcorp facility.

Section 11.17 summarizes the interpretation of A1C results during the screening visit for this study using the different A1C testing devices.

### 8.2.3 PHYSICAL ACTIVITY MONITORING

Participants will be provided an ActiGraph (either GT9X-BT link or CPIW) wrist monitor and asked to wear the device for 7-days of consecutive wear time at enrollment and once approximately every 1 month thereafter for the duration of the study. A reminder email, phone call, or text message one day prior to the scheduled event and on the day of event will be sent by our team.

Participants will return the ActiGraph device at the 12-month visit. If the actigraphy wrist monitor or accessories are damaged during a scheduled wear period, replacement device or accessories will be mailed to the participant.

[figure not shown]
The ActiGraph GT9X-BT Link and CPIW are FDA-cleared devices, which have the ability to distinguish non-wear time from physical inactivity. Both devices capture and record high resolution raw acceleration data, which are converted into a variety of objective activity measures. The CPIW, which is the newer model of the ActiGraph wrist monitor, has an extended 30-day battery life allowing

for continuous wear time during the scheduled wear period, which minimizes participant burden and the potential for missing data associated with frequent device charging. ActiGraph provides a cloud based service platform, CenterPoint, which allows automated capture of actigraphy data from the ActiGraph monitor. The participant will be blinded to the Actigraph data.

At the baseline visit, participants will be provided 1) the ActiGraph activity monitor, 2) Centrepoint (CP) data hub, 3) charging dock, 4) power cable and 5) USB Cable (see screenshot below), and a participant guide will be provided with clear instructions on how to use these devices. The CentrePoint data hub uses 3G cellular network (paid for by study team) to transmit data collected from the ActiGraph activity monitor to the study team via the CentrePoint cloud-based software. The participant's home WiFi will not be utilized for the remote data capture. The CentrePoint datahub uses Bluetooth technology to automatically capture data from the ActiGraph device when the participant is in close proximity to the datahub. Participants will also be asked to upload the raw data collected from the ActiGraph activity monitor to the CenterPoint data hub after each wear period by connecting the physical activity monitor to the data hub using a provided USB cable/charging dock (see screenshot below). This physical connection will provide the raw data required by the study team. The study team will track study participant compliance remotely using the CentrePoint software, which will indicate Bluetooth captured data as well as manual data upload to the data hub.

If the study team does not see that the participant is wearing their physical activity monitor, we will contact the participant by text message, email, or phone call to remind them to wear the device, ensure that the data hub is plugged in, and/or encourage the participant to upload data from their activity monitor to the datahub. If data show that fewer than 75% of the 7-day period comprised actual wear time, participants will be asked to repeat the consecutive 7-day period as soon as this is noted, and the previously collected incomplete/invalid data will be disregarded. Once the participant has been deemed compliant, a message or email will be sent to communicate that they have satisfactorily completed their 7-day wear period.

This screenshot shows the accessories that will be provided to study participants at the baseline visit for physical activity tracking.

This screenshot shows the connection between the activity monitor/charging dock to the CP Data hub, which will occur after every 7-day wear period to upload raw data to the Centerpoint cloud software, which is accessible by the study team.

The approach outlined above would allow the study participant to keep the activity monitor and accessories in their possession for the full duration of the trial (Section 8.2.3.1). If, for some reason, this approach is technically challenging for some participants or we find poor adherence with this strategy, we may elect to have study participants mail back their activity monitor each month as an alternative workflow (see Section 8.2.3.2.).

#### 8.2.3.1 PARTICIPANT KEEPS ACTIVITY MONITOR IN POSSESSION

Participant is provided an actigraph monitor at baseline visit together with charging device and accessories. Participant keeps the actigraph monitor in their possession between the baseline visit and 6 month visit, and charges the device as instructed between each wear period. A new or same device is provided at the 6 month visit and the participant again keeps the actigraph monitor in the possession between the 6 month visit and the 12 month visit.

#### 8.2.3.2 PARTICIPANT RETURNS ACTIVITY MONITOR VIA MAIL EACH MONTH

Participants are provided only a charged activity monitor prior to each wear period and asked to return the device via mail after each successful wear period. Participants will be provided a return postage paid mailer and asked to mail back the activity monitor after they receive confirmation from our study team that they have successfully completed the 7 day wear period. Once the device is received by the study team, the raw data will be downloaded and the device will be charged. The activity monitor will then be mailed back to the study participant at the time of their next wear period together with a postage paid return mailer for them to return the device after confirmation by our study team that they have successfully completed the 7-day wear period. The main barrier to Option #2 is the burden of participant mailing the monitor. We will make this process as simple as possible for study participants by providing postage paid mailers and clear instructions on how to return the device.

